6.1.1.2. Sensitivity/Supplementary Analyses

A sensitivity analysis will be performed for the Bayesian Emax model on the primary endpoint. The same Bayesian Emax model analysis as in Section 6.1.1.1 will be performed and reported, applied to the Censored Analysis Set (as described in Section 4), but using a vague prior for the placebo change from baseline at Week 12 (E₀). This will be a t-distribution with a mean of 0 and a standard deviation equal to 10 times the predicted standard deviation, i.e. t(Mean = 0, SD = 49, df=5).

An exploratory analysis for the primary endpoint, will be performed to estimate the treatment effect related to Estimand 1b (as described in Section 2.2.1). The same summaries and analysis as in Section 6.1.1.1 (except the additional week 12 only plots of LS means and differences) will be performed and reported, but applied to the Complete Analysis Set (as described in Section 4).

A supplementary analysis will be performed for the percent change from baseline in body weight, using an MMRM model as described in Section 5.2.3. All post-treatment dosing timepoints up to Week 12 (ie. Weeks 4, 8 and 12) will be included in the model. Additional terms for type of therapy [i.e. platinum or not] and type of cancer will be fitted in the model.

An additional supplementary analysis will be performed for the percent change from baseline in body weight at Week 12 only, by summarizing descriptively by treatment group (as described in Section 5.2.2) based on the following categories:

3-Categories 5-Categories

≥ 1% loss: ≥ 3.5% loss: %CFB ≤ -3.5 %CFB ≤ -1 -1 > %CFB < 1 ≥ 1% loss: -3.5 > %CFB ≤ -1 Stable: ≥ 1% gain: %CFB ≥1 Stable: -1 > %CFB < 1 ≥ 1% gain: 1 ≤ %CFB < 3.5

≥ 3.5% gain: %CFB ≥3.5

Barcharts of these percentages of participants in each category at Week 12 will also be produced, with all treatments on the same plot (one plot for the 3-category definition and one for the 5-category definition).

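### Three weight-change category conditions in SAP 6.1.1.2 have the lower-bound sign reversed, so the supplementary categories leave a gap and overlap

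*SAP*

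**What the plan says.** SAP 6.1.1.2 introduces the table with these words: "An additional supplementary analysis will be performed for the percent change from baseline in body weight at Week 12 only". Participants are counted by treatment group in a 3-category and a 5-category scheme, and the section adds: "Barcharts of these percentages of participants in each category at Week 12 will also be produced".

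The 5-category conditions are:
- "≥ 3.5% loss: %CFB ≤ -3.5"
- "≥ 1% loss: -3.5 > %CFB ≤ -1"
- "Stable: -1 > %CFB < 1"
- "≥ 1% gain: 1 ≤ %CFB < 3.5"
- "≥ 3.5% gain: %CFB ≥3.5"

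In the extracted text the 3-category conditions have run together, so the loss and Stable cells read "CFB ≤ -1 -1 > %CFB < 1". The remaining 3-category condition is a gain of 1% or more. Neither document defines these categories anywhere else, so this list is the specification a programmer would work from.

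**The concern.** A category scheme for one continuous variable should place every value in exactly one category. Here the middle condition asks for a value that is both below -1 and below +1, which is simply a value below -1. The Stable label is therefore attached to participants who lost weight, and participants whose weight barely moved have no category. The 5-category ≥ 1% loss line has the same fault: it asks for a value below -3.5 and at or below -1, which is simply a value below -3.5.

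At stake are a table and two bar charts. In a cachexia trial, the split between stable weight and lost weight is what a reader would take from them. A programmer who follows the text produces wrong counts. One who silently corrects it produces right counts that no longer match the written plan.

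**Working it through.** No stated figure needs reproducing; the check is interval logic.

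**Step 1. Reduce each printed condition** (x = percent change from baseline).
- Stable, both schemes: x < -1 and x < 1, so x < -1.
- ≥ 1% loss, 5 categories: x < -3.5 and x ≤ -1, so x < -3.5.
- All other conditions are as printed and behave as their labels say.

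**Step 2. Apply the literal conditions to ranges of x.**

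| x | 3 categories | 5 categories |
|---|---|---|
| below -3.5 | loss and Stable | ≥ 3.5% loss, ≥ 1% loss and Stable |
| exactly -3.5 | loss and Stable | ≥ 3.5% loss and Stable |
| above -3.5, below -1 | loss and Stable | Stable only |
| exactly -1 | loss | none |
| above -1, below 1 | none | none |
| 1 to below 3.5 | gain | ≥ 1% gain |
| 3.5 or more | gain | ≥ 3.5% gain |

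Single values: 0% meets no category in either scheme; -2% is loss and Stable in one scheme and Stable only in the other; -8% meets two categories and three.

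**Step 3. Count on a grid** from -20% to +20% in steps of 0.01 (4001 values).
- 3 categories, as printed: 199 values in none, 1902 in one, 1900 in two.
- 5 categories, as printed: 200 in none, 2150 in one, 1 in two, 1650 in three.
- With the three signs reversed: all 4001 values in exactly one category, in both schemes.

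**Step 4. Illustrate the size.** The documents do not give the Week 12 distribution in this trial. Assume it is normal with distribution function F, mean -1% to 5.81% and SD 5% to 7%. The upper mean, and an SD of 5.87% inside the range, are the Week 12 values from the single-arm Phase 1b study C3651009 (Protocol 2.2.1.1); the rest of the range is assumed.
- Unclassified: F(1) - F(-1).
- Meets the literal Stable rule: F(-1).
- 3-category total: 2F(-1) + 1 - F(1).
- 5-category total: 3F(-3.5) + [F(-1) - F(-3.5)] + 1 - F(1).

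At mean 5.81 and SD 5.87, F(1) = 0.206, F(-1) = 0.123 and F(-3.5) = 0.056. This gives:
- unclassified: 0.206 - 0.123 = 0.083;
- literal Stable: 0.123;
- 3-category total: 0.246 + 0.794 = 1.040;
- 5-category total: 0.168 + 0.067 + 0.794 = 1.029.

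Over the whole assumed range:
- unclassified: about 8% to 16%;
- literal Stable: about 9% to 50%;
- 3-category total: about 100% to 139%;
- 5-category total: about 98% to 161%.

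The gap and the overlap can offset each other. At mean 5.81 and SD 5 the totals are 100.5% and 98.1%, so a check that percentages add to roughly 100 would not reliably expose the fault.

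**The case against.** The strongest reply is that nobody would program this literally. Each condition sits beside a plain label, the outer conditions are one-sided and correct, and the ≥ 1% gain line has its lower bound the right way round. Together they leave one sensible partition, and a 5% loss cannot sensibly be called stable. This stands as a statement of intent and keeps the point minor. It does not make the printed conditions right.

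A second reply is that the table text is damaged: two side-by-side columns were merged, and placing the condition in the 3-category Stable row is an inference. That is fair, and the symbols should be checked against the original PDF. A reading fault is nevertheless unlikely. The same reversal occurs three times, while the other signs in the list, including the lower bound of the gain line, came through consistent with their labels.

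A reader might infer more than the documents support, in two ways.
- **That the primary endpoint results are at risk.** The primary endpoint is absolute change in kg, analysed by MMRM and the Bayesian Emax model (SAP 6.1.1.1). The affected output is a descriptive summary of percent change with no test attached. The percent-change MMRM in the same section does not use the categories. The ≥ 3.5% responder analysis is defined separately (SAP 3.4.13 and 6.4.13), and its cut is coded correctly in SAP Appendix 4.
- **That the repetition shows a deliberate rule.** Repetition fits a copied sign error equally well, and the labels and the correct gain line point that way.

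**Conclusion.** The point holds as a notation error in three printed conditions: Stable in the 3-category scheme, Stable in the 5-category scheme, and ≥ 1% loss in the 5-category scheme. As printed, neither scheme covers all values and neither is mutually exclusive. That conclusion follows from the conditions alone and needs no distributional assumption. The percentages in Step 4 do need one: they rest on normality and an assumed range of means and SDs, and show only that the effect would be visible if the text were programmed as it stands.

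The consequence is confined to a supplementary descriptive table and its bar charts. No estimate, interval, p-value or decision rule depends on it. Priority is low, but the correction should be made because the text is the only definition of these categories.

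**What to change.** In SAP 6.1.1.2 print:
- Stable, 3 categories: `-1 < %CFB < 1`
- Stable, 5 categories: `-1 < %CFB < 1`
- ≥ 1% loss, 5 categories: `-3.5 < %CFB ≤ -1`

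All three must change. Correcting only two leaves at least one scheme with a gap or an overlap. Add a programming check that each non-missing Week 12 value falls in exactly one category of each scheme, with test values at -3.5, -1, 0, 1 and 3.5. A check on the percentage total alone is not enough.

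The cost is one sign in each of three conditions. It needs no new data and no change to the design, the estimands or any model. If the tables have already been programmed, confirm which version of the conditions was used and record it.

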6.2. Secondary Endpoint(s)

6.2.1. Change from baseline in physical activity and gait endpoints measured with remote digital sensors at Week 12

Absolute values and changes from baseline in the physical activity and gait endpoints (listed in Section 3.2.1) will be summarized descriptively by treatment group and timepoint, as described in Section 5.2.1. Tables will include baseline and all post-baseline timepoints.

Change from baseline in the physical activity and gait endpoints will be analyzed using an MMRM model as described in Section 5.2.3. All timepoints up to Week 12 will be included in the model. Additional terms for type of therapy [i.e. platinum or not] and type of cancer will be fitted in the model. This will be used to estimate the treatment effect related to Estimand 2 (as described in Section 0).

Additionally, the amount of available physical activity and gait data will be summarized descriptively by treatment group and timepoint, as described in Section 5.2.2. If it is deemed that the amount of available data is insufficient or too imbalanced across the treatment groups, the results of the MMRM analysis may not be included in the CSR.

6.2.2. Change from baseline in FAACT sub-scale scores at Week 12

FAACT-ACS and FAACT-5IASS will be summarized and analyzed in a similar way to the secondary endpoint described in Section 6.2.1, These analyses will estimate the treatment effect related to Estimand 3 (as described in Section 0).

6.2.3. Change from baseline score for each of the questions from the CRCSD at Week 12

- Anorexia/appetite;
- Nausea:
- Vomiting;
- Fatigue

Weekly average data for each of the CRCSD endpoints will be summarized and analyzed in a similar way to the secondary endpoint described in Section 6.2.1. These analyses will estimate the treatment effect related to Estimand 4 (as described in Section 0).

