#### 9.3.3. Secondary Endpoints Analysis

Endpoint	Statistical Analysis Methods

 
Change from baseline in each of the physical activity and gait endpoints at Week 12:
 
Moderate to vigorous physical activity time;
 
Sedentary activity time;
 
Non sedentary activity time;
 
Total vector magnitude;
 
Mean activity level during M6min;
 
Mean gait grand;
 
	Change from baseline in physical activity and gait endpoints will be analyzed separately using Estimand 2 and an MMRM model (as per Section 9.3.1.1). The MMRM model will be fitted to the change from baseline at all post-treatment timepoints up to Week 12 using the Censored analysis set.

 
Mean gan speed,
 
95th percentile gait speed.
 
	Least squares means (and 90% CIs) and mean differences versus placebo (and 90% CIs and p values) will be provided. No adjustments will be made for multiplicity.

 
Change from baseline in each of the FAACT sub-scale scores at Week 12:
 
FAACT-ACS;
 
FAACT-5IASS.
 
	Change from baseline in FAACT sub-scale scores will be analyzed separately using Estimand 3 and an MMRM model (as per Section 9.3.1.1). The MMRM model will be fitted to the change from baseline at all post-treatment timepoints up to Week 12 using the Censored analysis set.
	Least squares means (and 90% CIs) and mean differences versus placebo (and 90% CIs and p values) will be provided. No adjustments will be made for multiplicity.

 
Change from baseline for each of the questions from the CRCSD at Week 12:
 
Anorexia/appetite;
 
Nausea and vomiting;
 
Fatigue.
 
	Change from baseline in questions from the CRCSD will be analyzed separately using Estimand 4 and an MMRM model (as per Section 9.3.1.1). The MMRM model will be fitted to the change from baseline weekly averages at all post-treatment timepoints up to Week 12 using the Censored analysis set.
	Least squares means (and 90% CIs) and mean differences versus placebo (and 90% CIs and p values) will be provided. No adjustments will be made for multiplicity.

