2.1. Modifications to the Analysis Plan Described in the Protocol

Not applicable.

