 64, the Week 8 average will be taken over Days 57 to 63 only)
- Week 10: Starting on the Week 10 visit day and ending +7 days later or on the day before the start day for the Week 12 average (e.g. if the Week 10 visit day is Day 71, the Week 10 average will be taken over Days 71 to 78; however, if the Week 12 start date is Day 77, the Week 10 average will be taken over Days 71 to 76 only)
- Week 12: Starting on the Week 12 visit day -8 days, and ending on the day before the Week 12 visit day (e.g. if the Week 12 visit occurs on Day 85, the Week 12 average will be taken over Days 77 to 84).

If fewer than 3 days of data are recorded on the lumbar device, the average should be treated as missing. If fewer than 3 compliant days of data are recorded on the wrist device, the average should be treated as missing (a day is defined as compliant if at least 7 hours of awake wear or 18 hours of total wear time are present).

Baseline is defined as the mean taken over the 8 days of wear during screening, i.e. Day 1 weekly average (as described above). Change from baseline will be calculated for all post-baseline weekly averages.

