5. GENERAL METHODOLOGY AND CONVENTIONS

5.1. Hypotheses and Decision Rules

The null hypothesis of no difference between ponsegromab and placebo will be tested for each primary, and selected secondary (physical activity, FAACT and CRCSD) and tertiary (PROMIS-fatigue, PROMIS-physical function, LSMI and survival status) endpoints. The alternative hypothesis is that ponsegromab is superior to placebo. The Type I error rate (α-level) used for the statistical inference will be 5% (1-sided). Each dose of ponsegromab will be compared separately with placebo. No adjustment for multiple comparisons will be made.

For all other endpoints, the results of any statistical analyses are for exploratory purposes only and there is no formal hypothesis testing.

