5.2.3. Mixed Models Repeated Measures (MMRM) Analysis

The MMRM model will include participant as a random term, and baseline, time (as a factor), baseline-by-time interaction, treatment and treatment-by-time interaction as fixed terms in the model. An unstructured covariance matrix will be fitted to the repeated times within subject (other covariance matrices will be considered if necessary), and the Kenward Roger approximation will be used for estimating degrees of freedom. Additional terms may be fitted in the model (eg, type of therapy [ie, platinum or not], type of cancer), as appropriate.

Least-squares (LS) means (and 90% CIs) and LS mean differences versus placebo (and 90% CIs, and p-values for primary and selected secondary/tertiary endpoints), at each timepoint, will be provided. No adjustments will be made for multiplicity. In addition, profile plots of the LS means and differences (and 90% CIs for both) will be produced over time, with a separate line for each treatment group.

Standard SAS output will be provided to support the statistical summary table for the analysis model but will not be included in the CSR.

Example SAS code is provided in Appendix 4.

Statistical Model Diagnostics

The presence of outliers will be investigated for this model. An outlier will be defined as any response data value with a studentized (conditional) residual greater than 3, or less than 3. A listing will be presented of any participants meeting these criteria and will be included with standard SAS output. The assumptions of normality will be verified graphically using

residual plots. For each fitted model, a set of conditional studentized residual plots will be produced, including residual plot, histogram of normality, quartile-quartile (QQ) plot and summary of fit statistics. The residual plots will not be included in the CSR.

If there are outliers or major deviations from normality, then the effect of these on the conclusions may be investigated through alternative transformations and/or analyses excluding outliers. Justification for any alternative to the planned analysis will be given in the report of the study.

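### SAP 6.2.1 lets the MMRM results for the seven digital secondary endpoints be left out of the CSR on an undefined judgement about data availability, although the protocol promises them and the SAP declares no departure

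*SAP*

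**What the plan says.** **The commitment.** For the physical activity and gait endpoints, protocol 9.3.3 says: "Least squares means (and 90% CIs) and mean differences versus placebo (and 90% CIs and p values) will be provided". No condition is attached. SAP 5.2.3 promises the same kind of output for every MMRM: "Least-squares (LS) means (and 90% CIs) and LS mean differences versus placebo", with intervals, and with p-values for the primary and selected other endpoints. SAP 5.1 counts these endpoints among those formally tested, in its list of "selected secondary (physical activity, FAACT and CRCSD" endpoints. SAP 6.2.1 states that the MMRM is what estimates the treatment effect for Estimand 2.

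**The permission to omit.** The last paragraph of SAP 6.2.1 says that "the amount of available physical activity and gait data will be summarized descriptively by treatment group and timepoint". If the data are then judged "insufficient or too imbalanced across the treatment groups, the results of the MMRM analysis may not be included in the CSR".

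**The declared departures.** SAP 2.1, which lists modifications to the protocol's analysis plan, reads "Not applicable".

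**The only numeric rules on sensor data.** These are in SAP 3.2.1 and work at participant level. For the wrist device: "If fewer than 3 compliant days of data are recorded on the wrist device, the average should be treated as missing". The lumbar device has a similar three-day minimum. Neither rule governs whether a model is reported.

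**The concern.** A prespecified result for a tested secondary endpoint should reach the study report whatever it shows. The clause makes that depend on a judgement with no stated standard, and nothing separates the judgement from knowledge of the result. The clause does not deal with a model that fails: the analysis has been run, and it is its results that may be omitted.

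At stake are the estimates that answer the digital-sensor objective. If they are absent, the reader has arm-level means and a table of how much data there was. The covariate-adjusted differences from placebo, their 90% intervals and their p-values would be missing. The reader could not tell whether the omission was driven only by data quantity, because no criterion exists to check it against.

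**Working it through.** The point rests on comparing texts. The plan states no figure for it, so there is none to reproduce.

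**1. Scope.** SAP 3.2.1 lists seven digital secondary endpoints: moderate-to-vigorous activity time, sedentary time, non-sedentary time, total vector magnitude, mean activity in the most active six minutes, mean gait speed, and 95th percentile gait speed. SAP 5.1 compares each of three doses separately with placebo. 7 × 3 = 21 Week 12 comparisons.

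**2. What the clause specifies.**

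| Element | SAP 6.2.1 |
|---|---|
| Trigger | Too little data, or too much imbalance between groups |
| Cut-off for either | None |
| Who decides | Not stated |
| When | Not stated |
| Blind to treatment or to MMRM results | Not required |
| Consequence | MMRM results may be left out of the CSR |

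Sufficiency could be judged on pooled data. Imbalance cannot; it needs data split by arm. Masked arm labels would serve, but the SAP does not ask for them.

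**3. How the SAP treats other judgements.**
- SAP 2.2.1 and section 4 have prohibited procedures and medications classified from blinded listings before database lock. The clause in 6.2.1 has no equivalent.
- SAP 5.2.4, 5.2.7 and 6.5 allow an analysis to be simplified or not performed when the model cannot be fitted, is inappropriate, or is not supported by the data. In 6.2.1 the ground is the amount and balance of data, and what may be withheld is a result already obtained.
- SAP 7.2.1 provides, if an interim is held, for MMRM analyses of gait speed, 95th percentile gait speed, moderate-to-vigorous activity and sedentary time. By-dose results for four of the seven endpoints could then exist before the final judgement. The SAP does not say that the decision-maker must be unaware of them.

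**4. What remains if the clause is used.** Under SAP 6.2.1 and 5.2.1, absolute values and changes from baseline are still summarised by arm and visit, and so is data availability. Neither carries a permission to omit. The loss is confined to the model-based estimates, intervals and p-values.

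**5. Why a cut-off matters (illustration only).** Inputs: four arms of 42 (protocol 9.5). Assumptions that are not in the documents: the same true availability in every arm, between 50% and 80%, and gaps of 15 or 20 percentage points as examples of imbalance. The number with data in each arm was drawn from Binomial(42, p), and the gap is the best arm's proportion minus the worst arm's. There were 400,000 simulated trials per row.

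| True availability p | Gap ≥ 15 points | Gap ≥ 20 points |
|---|---|---|
| 50% | 48.7% | 24.7% |
| 60% | 46.8% | 22.8% |
| 70% | 40.6% | 17.7% |
| 80% | 28.2% | 9.2% |

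The protocol assumes about 30% discontinuation, so 100% − 30% = 70% is roughly the most availability to expect at Week 12 even with perfect sensor wear. Gaps of this size between arms are ordinary chance, and the clause does not say whether they would count.

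**The case against.** **The protocol allows the SAP to differ.** Protocol section 9 says so, and requires an amendment only for major changes to the primary endpoint or its analysis. The protocol also says the results will be provided without naming the CSR, and SAP 5.2.3 itself distinguishes output that is produced from output that enters the CSR. A reader might infer that the protocol's rules have been broken; they have not. What stands is that reporting is the natural meaning of protocol 9.3.3, and that SAP 2.1 does not list the departure.

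**The timing is not stated.** A reader might infer that the decision is to be taken after unblinding with the model output in view. The SAP does not say that. Version 3 is attributed to a blinded data review, and sufficiency could be judged blind. What stands is that nothing rules out a late or informed decision.

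**The descriptive results stay.** This is correct, and it limits the harm. Protocol 10.1.6 also promises complete reporting regardless of outcome. That general commitment does not remove a specific permission to omit.

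**Sparse or uneven data may make the MMRM misleading.** If wear depends on outcome, the missing-at-random assumption carried from Estimand 1 to Estimand 2 would fail. That is a reason for a caution beside the result. It does not favour the retained descriptive means, which are no better protected against such missingness.

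**Other endpoints.** FAACT-ACS and FAACT-5IASS "will be summarized and analyzed in a similar way to the secondary endpoint described in Section 6.2.1", and CRCSD and PROMIS use similar wording. A reader might infer that the omission clause extends to them. The text does not support this: the clause belongs to a paragraph about physical activity and gait data, and the cross-reference concerns summary and analysis, not a reporting exemption tied to sensor data.

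**Selection among comparisons.** A reader might measure the harm by the false positives expected among unadjusted tests. That number is the same with or without the clause. Because availability is set per device, the discretion probably works by device more than by individual comparison.

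**Conclusion.** The point holds for the seven digital secondary endpoints, 21 dose-placebo comparisons under Estimand 2. The SAP contains an explicit permission, without criterion, decision-maker or timing, to leave prespecified model-based results out of the CSR, and it does not declare this as a change from the protocol. The result is an undeclared departure with a selective-reporting risk. It does not show that results will be selected, and it does not breach the protocol's rules on what the SAP may change.

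The consequence is moderate: these are unadjusted Phase 2 secondary endpoints whose descriptive summaries by arm stay reported. The conclusion rests on the wording alone and on reading the protocol's promise to provide results as a promise to report them. It does not depend on the chance-imbalance illustration or on any assumption about who wears the sensors.

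**What to change.** Delete the sentence in SAP 6.2.1 that permits omission. In its place, state that:

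- the MMRM results for all seven digital secondary endpoints are always reported in the CSR, beside the table of available data;
- a caution accompanies any result where data are sparse or imbalanced between arms;
- if the model does not converge, the CSR says so and reports the simplified model that was fitted.

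If the sponsor prefers to keep a conditional rule, the minimum is a numeric cut-off, a named decision-maker, a decision taken before unblinding and before any MMRM result is seen, and an entry in SAP 2.1. Unconditional reporting is simpler.

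The cost is one paragraph of the SAP, and some imprecise estimates in the CSR whose width the 90% intervals will show. No additional data or analysis is needed, since the MMRM is already planned.
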